12.3 Determination of sample size

This is a regulatory commitment study to investigate the safety profile and to describe the cumulative incidence of major cardiovascular events of ticagrelor including fatal/life-threatening bleeding among Taiwanese NSTEMI patients within 1 year of follow up. If the fatal/life-threatening bleeding rate is 5% then 100 patients would allow to **describe the safety profile** estimated with a precision of +/-4.3%, with a 95%CI.

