3.1.2 Enrolment

Male and female patients with NSTEMI, fulfilling all of the inclusion criteria (see Section 4.1) and none of the exclusion criteria (see Section 4.2) can be enrolled in this study.

Approximately 100 patients at approximately 8 study centres will be enrolled.

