3.2.4 Limitations of the study

The results of the phase IV study will be descriptive, and due to the small population of this study, there can be no formal statistical comparison to the data from the comparison of ticagrelor to clopidogrel in the PLATO study. However, the Kaplan-Meier% with 95% CI for the both studies will be presented.

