5.9 Withdrawal from study

Subjects are at any time free to withdraw from study (investigational product and assessments), without prejudice to further treatment (withdrawal of consent). Such subjects will always be asked about the reason(s). If possible, they will be seen and assessed by an investigator; final visits should be 1 week after the discontinuation (See Table 2). Adverse events will be followed up by the investigator for as long as medically indicated, but without further recording in the eCRF); and all study drugs should be returned by the subject.

The Investigator should always ask the patient to allow contact 12 months after enrolment for a final follow-up to ascertain AEs even if participation in other visits is not agreed. At a minimum, permission to ascertain vital status should be obtained if at all possible. This agreement should be noted and signed by both the Investigator and the patient on the Informed consent form, as well as entered in the medical records. The reason for discontinuation and the date of discontinuation from the study must be documented in the eCRF.

Withdrawn subjects will not be replaced.

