12.2.2 Primary objective-primary safety endpoint

Statistical methods will be descriptive. For continuous data, descriptive statistics will be presented as number of patients (n), mean, standard deviation (SD), median, minimum and maximum. For categorical data, the frequency and percentage of patients in each category will be presented. Counts that are zero will be displayed as "0". Percentages will be based on non-missing data unless otherwise specified.

Patients will be censored at 7 days after their last dose of ticagrelor. Patients who withdraw consent to participate in the study will be included up to the date of their study termination.

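### The ±4.3-point precision in section 12.3 is a symmetric large-sample half-width at about 5 expected events, and it is too favourable on the upper side

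*Protocol*

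**What the plan says.** Protocol section 12.3 describes the study as a regulatory commitment and then gives its only precision statement. The condition is "If the fatal/life-threatening bleeding rate is 5% then 100 patients would allow to" describe the safety profile, and the result is a rate "estimated with a precision of +/-4.3%, with a 95%CI". The population and time frame are "among Taiwanese NSTEMI patients within 1 year of follow up". Section 12.3 does not name the interval method, and it gives the precision as a single plus-or-minus value.

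Related text:
- Section 3.1.2 gives the size: "Approximately 100 patients at approximately 8 study centres will be enrolled".
- Section 12.2.2 plans the safety summary as counts and percentages ("the frequency and percentage of patients in each category will be presented") and names no interval method.
- Section 3.2.4 says "The results of the phase IV study will be descriptive" and rules out formal comparison with PLATO because the study is small.
- Table 1 in section 1.3 gives Kaplan-Meier rates of fatal/life-threatening bleeding on ticagrelor: 5.8% in PLATO overall, 6.8% in the Asian subgroup and 4.9% in Taiwan (2 events in 44 patients).

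**The concern.** A 5% rate in 100 patients means about 5 events. With so few events near zero, the sampling distribution is skewed. An equal plus-or-minus margin then reaches too far down and not far enough up. A precision labelled 95% should be about what a sound 95% interval would deliver, on both sides of the estimate.

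The study is descriptive and tests no hypothesis, so the width of the interval is the statistical content of the sample-size section. For a bleeding endpoint the upper limit is the informative one: it shows how high a rate would remain compatible with the data. If that side is understated, the regulator and ethics committees are told that 100 patients will pin down the rate more closely than they will.

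**Working it through.** **Inputs.** Rate p = 0.05 and n = 100, both from section 12.3. The 95% level is taken as two-sided. All 100 patients are treated as fully observed, because section 12.3 allows for no loss.

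**Step 1: reproduce the stated figure.** The Wald half-width is z × √(p(1 − p)/n) = 1.960 × √(0.05 × 0.95/100) = 1.960 × 0.02179 = 0.0427, or 4.27 points. This rounds to the stated 4.3 and implies limits of 0.73% and 9.27%. A t quantile on 99 degrees of freedom gives 4.32, which also rounds to 4.3 and is the same kind of large-sample formula. With a continuity correction the half-width is 4.77, which does not match. None of the small-sample intervals in Step 3 gives a symmetric 4.3.

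**Step 2: how often does this interval contain the true rate?** Let X be Binomial(100, 0.05), and compute the Wald interval for each possible count.
- At X = 2 the upper limit is 2 + 196 × √(0.02 × 0.98/100) = 4.74%, below 5%. At X = 3 it is 6.34%. The interval therefore lies wholly below the true rate when X ≤ 2, and P(X ≤ 2) = 0.0059 + 0.0312 + 0.0812 = 0.118.
- At X = 11 the lower limit is 4.87%, and at X = 12 it is 5.63%. The interval lies wholly above the true rate when X ≥ 12, and P(X ≥ 12) = 0.004.
- Coverage is 1 − 0.118 − 0.004 = 0.877 to 0.878, about 88%.

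The nominal miss is 2.5% on each side. Here 11.8% of trials would have an upper limit below the true rate, and 0.4% a lower limit above it.

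The same enumeration at other rates, with n = 100:

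| True rate | Wald coverage | True rate above the upper limit |
|---|---|---|
| 3% | 80.2% | 19.5% |
| 4% | 90.6% | 8.7% |
| 5% | 87.7% | 11.8% |
| 5.8% (PLATO overall) | 92.9% | 6.6% |
| 6.8% (PLATO Asian) | 90.7% | 8.5% |

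Coverage oscillates with the rate but is below 95% at every rate checked.

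**Step 3: what do small-sample intervals give at 5/100?**

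| Method | 95% interval | Above the estimate |
|---|---|---|
| Wald | 0.73% to 9.27% | +4.27 |
| Jeffreys | 1.93% to 10.61% | +5.61 |
| Mid-P | 1.86% to 10.73% | +5.73 |
| Wilson | 2.15% to 11.18% | +6.18 |
| Clopper-Pearson | 1.64% to 11.28% | +6.28 |
| Agresti-Coull | 1.87% to 11.46% | +6.46 |
| Log-log, no censoring | 2.11% to 11.60% | +6.60 |

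Two of these can be checked directly.
- Clopper-Pearson: the limits solve P(X ≥ 5 | p) = 0.025, giving p = 1.64%, and P(X ≤ 5 | p) = 0.025, giving p = 11.28%.
- Wilson: the centre is (0.05 + 3.8415/200)/(1 + 3.8415/100) = 6.66%, and the half-width is 1.960 × √(0.000475 + 3.8415/40000)/1.0384 = 4.51 points, giving 2.15% to 11.18%.

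**Step 4: a second scenario.** With 7 events in 100, near the Asian rate of 6.8%, the Clopper-Pearson interval is 2.86% to 13.89%.

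**Step 5: scale.** For the upper limit to stay within 4.3 points of a 5% estimate, about 179 patients would be needed by Clopper-Pearson or 176 by Wilson. This only shows the size of the gap; it is not a proposed sample size.

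**The case against.** The case for leaving the text alone is that this is a planning approximation in a descriptive study. The figure follows from the protocol's own inputs, the text is explicitly conditional on a 5% rate, and section 3.2.4 openly names the small population. The regulator required the study, and nothing in its conduct turns on whether the upper limit is 9.3% or 11.3%. Clopper-Pearson is also conservative (98.3% coverage at this rate and size), so setting +6.3 against +4.3 sharpens the contrast. The 88% belongs to one point on an oscillating curve.

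Much of that stands, and it limits the point. It does not rescue the figure. The mildest interval in the table, Jeffreys, still reaches 5.6 points above the estimate, and Wald coverage is below 95% at every rate checked.

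A reader might infer several stronger things that the documents do not support:
- **That 4.3 is an arithmetic error.** It is not; it reproduces from the stated inputs.
- **That the protocol claims to rule out rates above 9.3%.** Section 12.3 gives an expected precision and sets no threshold, exclusion claim or decision rule.
- **That a definite amount of information is lost.** Section 5.9 says "Withdrawn subjects will not be replaced" and section 12.2.2 censors safety follow-up 7 days after the last dose. However, no loss rate is given, so an effective sample size cannot be derived.
- **That the efficacy precision is misstated.** Section 12.3 states none.
- **That the analysis will use a Wald interval.** The protocol names no method for it, and that choice commonly sits in the SAP.
- **That 100 patients is the wrong number.** The point concerns what is said about that number.

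**Conclusion.** The point holds as a criticism of one planning statement. The ±4.3 points in section 12.3 is a symmetric large-sample half-width carrying a 95% label that it does not earn at about 5 expected events. Its coverage is about 88% at a 5% rate, and 80% to 93% across the rates checked from 3% to 6.8%. At 5% nearly all misses have the true rate above the upper limit. Standard intervals at 5/100 extend 5.6 to 6.6 points above the estimate, so the upper-side uncertainty is understated by about 1.3 to 2.3 points (5.61 − 4.27 = 1.34; 6.60 − 4.27 = 2.33).

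These figures assume independent patients, a simple proportion, a two-sided 95% level and complete one-year follow-up of all 100 patients. The consequence is moderate: the protocol misinforms its readers about the upper side of its only stated precision, but no test, decision rule or conduct of the study depends on it.

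**What to change.** Keep 100 patients and replace the plus-or-minus figure in section 12.3 with an asymmetric interval that names its method. Suggested wording:

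> With 5 events in 100 patients (5%), the exact (Clopper-Pearson) 95% confidence interval is 1.6% to 11.3%, assuming complete follow-up. With 7 events, near the PLATO Asian rate of 6.8%, it is 2.9% to 13.9%.

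Another standard small-sample interval, such as Wilson, would serve equally well if it is named. The cost is a sentence or two and a stated precision that looks less favourable. Sample size, conduct and data collection are unchanged.

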12.4 Data monitoring committee (Not applicable)

13. IMPORTANT MEDICAL PROCEDURES TO BE FOLLOWED BY THE INVESTIGATOR

13.1 Medical emergencies and AstraZeneca contacts

The Principal Investigator is responsible for ensuring that procedures and expertise are available to handle medical emergencies during the study. **A medical emergency usually constitutes an SAE and is to be reported as such, see Section 6.4.4**

In the case of a medical emergency the investigator may contact the Study Delivery Team Leader. If the Study Delivery Team Leader is not available, contact the Study Delivery Team Physician at the AstraZeneca Research and Development.

[REDACTED]	[REDACTED]	[REDACTED]
[REDACTED]	[REDACTED]	[REDACTED] [REDACTED] [REDACTED]
[REDACTED]	[REDACTED]	[REDACTED] [REDACTED] [REDACTED] [REDACTED]

13.2 Overdose

An overdose of ticagrelor is defined as intake of 4 or more ticagrelor tablets (360 mg)/day.

In the event of an overdose of ticagrelor, the investigator must ascertain the time and extent of the overdose regardless of severity. The investigator should determine the causative circumstance and whether haemorrhagic or toxic complications have occurred or are likely to do so. Depending on these facts it must be decided whether the patient should be hospitalised for observation or not.

Bleeding is one of the most likely pharmacological effects of excessive ticagrelor dosing, and appropriate supportive measures such as volume replacement, local haemostatic measures, and decompression or drainage may be required depending on the extent of bleeding or volume of blood lost. Patients with overdose-related bleeding should be cautioned to avoid unnecessary activity, mechanical tissue stress, and minor trauma for at least 24 hours after the bleeding has stopped. For other symptoms that can be expected after an overdose of ticagrelor and additional information can be found in the package insert for ticagrelor.

An overdose with associated AEs is recorded as the AE diagnosis/symptoms on the relevant AE modules in the eCRF and on the Overdose eCRF module.

An overdose without associated symptoms is only reported on the Overdose eCRF module.

If an overdose on an AstraZeneca study drug occurs in the course of the study, then investigators or other site personnel inform appropriate AstraZeneca representatives immediately, or **no later than 24 hours** of when he or she becomes aware of it.

The designated AstraZeneca representative works with the investigator to ensure that all relevant information is provided to the AstraZeneca Patient Safety data entry site.

For overdoses associated with SAE, standard reporting timelines apply, see Section 6.4.4. For other overdoses, reporting should be done within 30 days.

13.3 Pregnancy

All outcomes of pregnancy should be reported to AstraZeneca.

13.3.1 Maternal exposure

If a subject becomes pregnant during the course of the study investigational product should be discontinued immediately.

Pregnancy itself is not regarded as an adverse event unless there is a suspicion that the investigational product under study may have interfered with the effectiveness of a contraceptive medication. Congenital abnormalities/birth defects and spontaneous miscarriages should be reported and handled as SAEs. Elective abortions without complications should not be handled as AEs. The outcome of all pregnancies (spontaneous miscarriage, elective termination, ectopic pregnancy, normal birth or congenital abnormality) should be followed up and documented even if the subject was discontinued from the study.

If any pregnancy occurs in the course of the study, then investigators or other site personnel inform appropriate AstraZeneca representatives immediately, or **no later than 24 hours** of when he or she becomes aware of it.

The designated AstraZeneca representative works with the investigator to ensure that all relevant information is provided to the AstraZeneca Patient Safety data entry site within 1 or 5 days for SAEs, see Section 6.4.4 and within 30 days for all other pregnancies.

The same timelines apply when outcome information is available.

The PREGREP module in the eCRF is used to report the pregnancy and the PREGOUT is used to report the outcome of the pregnancy.

13.3.2 Paternal exposure

There are no restrictions against fathering a child when treated with ticagrelor. If paternal exposure pregnancy occurs in the course of the study, then investigators or other site personnel should inform appropriate AstraZeneca representatives immediately or no later than 24 hours as described in the maternal exposure Section 13.3.1.

